14.1. Planned Table Descriptions

The following are planned summary tables for protocol number NI-0501-09. The table numbers and page numbers are place holders only and will be determined when the tables are produced.

Table 15: Planned Tables

Table Number	Table Title / Summary	Population(s)	Supporting listing			
14.1 Demog	14.1 Demographic Data					
14.1.1.1	Summary of Patient Enrollment and Disposition	Enrolled Pop	16.2.1.1, 16.2.1.2			
14.1.1.2	Summary of Re-Treated Patients	All Treated Pop	16.2.1.1, 16.2.5.1			
14.1.2	Summary of Protocol Deviations	Enrolled Pop Excluding Screen Failures	16.2.2.1			
14.1.3.1	Demographic Characteristics	All Treated Pop	16.2.4.1			
14.1.3.2	Baseline Characteristics	All Treated Pop	16.2.4.1			
14.1.4.1	HLH Disease Characteristics at Diagnosis	All Treated Pop	16.2.4.4, 16.2.4.5			
14.1.4.2	Medical History Other Than HLH Disease by System Organ Class and Preferred Term	All Treated Pop	16.2.4.2			
14.1.4.3	HLH Disease Characteristics at Screening/Baseline	All Treated Pop	16.2.4.11, 16.2.4.12			
14.1.5	Summary of Previous HLH Treatment by ATC Level 1 and Level 2	All Treated Pop	16.2.4.3			
14.1.6	Summary of Systemic Steroid Use Prior to First Emapalumab Infusion	All Treated Pop	16.2.4.3			
14.1.	Summary of Prior Medications Other Than HLH Treatment by ATC Level 1 and Level 2	All Treated Pop	16.2.4.6			
14.2 Efficac	zy Data					
14.2.1.1.1	Statistical Analysis of the Overall Response	All Treated Pop, Evaluable Pop	16.2.6.3			
14.2.1.1.2	Sensitivity Analysis 1: Overall Response at EOT or Week 8 (Whichever Occurs Earlier) With Deaths Considered as Non- Responders	All Treated Pop	16.2.6.3			
14.2.1.1.3	Sensitivity Analysis 2: Overall Response at EOT or Week 8 (Whichever Occurs Earlier) With Early Withdrawal Considered as Non-Responders	All Treated Pop	16.2.6.3			

[figure not shown]
[figure not shown]

Table Number	Table Title / Summary	Population(s)	Supporting listing
14.2.1.1.4	Sensitivity Analysis 3: Overall Response at EOT or Week 8 (Whichever Occurs Earlier) With Patients Who Receive Concomitant Administration of Other HLH Treatments Considered as Non-Responders	All Treated Pop	16.2.6.3
14.2.1.1.5	Sensitivity Analysis 4: Overall Response at EOT or Week 8 (Whichever Occurs Earlier) With Deaths, Early Withdrawals, and Patients Who Receive Concomitant Administration of Other HLH Treatment Considered as Non- Responders	All Treated Pop	16.2.6.3
14.2.1.1.6	Sensitivity analysis 5: Overall Response at EOT or Week 8 (whichever occurs earlier) with patients deemed as having a protocol deviation impacting statistical analysis removed	Evaluable Pop Without Major PDs	16.2.6.3
14.2.1.1.7	Supplementary Analysis: Overall Response at EOT or Week 8 (whichever occurs earlier) – Modified Definition	All Treated Pop	16.2.6.3
14.2.1.2	Overall Response Components: Complete Response, Partial Response, HLH Improvement, No Response	All Treated Pop, Evaluable Pop	16.2.6.3
14.2.1.3.1	Evolution of Clinical Signs Characterizing HLH Disease - Part 1	All Treated Pop, Evaluable Pop	16.2.6.1.1, 16.2.9.3.
14.2.1.3.2	Evolution of Clinical Signs Characterizing HLH Disease - Part 2	All Treated Pop, Evaluable Pop	16.2.9.4
14.2.2.1	Overall Survival	All Treated Pop, Evaluable Pop	16.2.6.2
14.2.2.2	Survival to HSCT	All Treated Pop, Evaluable Pop	16.2.6.2
14.2.2.3	Survival post HSCT	All Treated Pop, Evaluable Pop	16.2.6.2
14.2.3	Event-free Survival post HSCT	All Treated Pop, Evaluable Pop	16.2.6.2
14.2.4.1	Duration of Response	All Treated Pop, Evaluable Pop	16.2.6.2
14.2.4.2	Cumulative Duration of Response for Patients Achieving Overall Response	All Treated Pop, Evaluable Pop	16.2.6.1.1, 16.2.6.1.2, 16.2.6.1.3, 16.2.6.1.4.

premier research

Table Number	Table Title / Summary	Population(s)	Supporting listing
14.2.5	Time-to-Response	All Treated Pop, Evaluable Pop	16.2.6.2
14.2.6	Investigator Assessment of Clinical Response	All Treated Pop, Evaluable Pop	16.2.6.4
14.2.7.1	Summary of Dexamethasone Daily Dose (mg/m ²) Over Time	All Treated Pop, Evaluable Pop	16.2.5.3
14.2.7.2	Glucocorticoids Reduction	All Treated Pop, Evaluable Pop	16.2.6.3
14.2.7.3	Patients Proceeding to HSCT	All Treated Pop, Evaluable Pop	16.2.6.3
14.2.8.1	Summary of PedsQL Total Scale Score (Parent Reports) and Change from Baseline by Questionnaire Age Group	All Treated Pop, Evaluable Pop	16.2.6.8
14.2.8.2	Summary of PedsQL Physical Health Summary Score (Parent Reports) and Change from Baseline by Questionnaire Age Group	All Treated Pop, Evaluable Pop	16.2.6.8
14.2.8.3	Summary of PedsQL Psychosocial Health Summary Score (Parent Reports) and Change from Baseline by Questionnaire Age Group	All Treated Pop, Evaluable Pop	16.2.6.8
14.2.8.4	Summary of PedsQL Physical Functioning Scale Score (Parent Reports) and Change from Baseline by Questionnaire Age Group	All Treated Pop, Evaluable Pop	16.2.6.8
14.2.8.5	Summary of PedsQL Emotional Functioning Scale Score (Parent Reports) and Change from Baseline by Questionnaire Age Group	All Treated Pop, Evaluable Pop	16.2.6.8
14.2.8.6	Summary of PedsQL Social Functioning Scale Score (Parent Reports) and Change from Baseline by Questionnaire Age Group	All Treated Pop, Evaluable Pop	16.2.6.8
14.2.8.7	Summary of PedsQL Work/Study Functioning Scale Score (Parent Reports for Child >24 months) and Change from Baseline by Questionnaire Age Group	All Treated Pop, Evaluable Pop	16.2.6.8
14.2.8.8	Summary of PedsQL Physical Symptoms Scale Score (Parent Reports for Infants 1-24 months) and Change from Baseline by Questionnaire Age Group	All Treated Pop, Evaluable Pop	16.2.6.8
14.2.8.9	Summary of PedsQL Cognitive Functioning Scale Score (Parent Reports for Infants 1-24 months) and Change from Baseline by Questionnaire Age Group	All Treated Pop, Evaluable Pop	16.2.6.8
14.2.9.1	Summary of PedsQL Total Scale Score (Child Reports) and Change from Baseline by Questionnaire Age Group	All Treated Pop, Evaluable Pop	16.2.6.9

[figure not shown]

Table Number	Table Title / Summary	Population(s)	Supporting listing
14.2.9.2	Summary of PedsQL Physical Health Summary Score (Child Reports) and Change from Baseline by Questionnaire Age Group	All Treated Pop, Evaluable Pop	16.2.6.9
14.2.9.3	Summary of PedsQL Psychosocial Health Summary Score (Child Reports) and Change from Baseline by Questionnaire Age Group	All Treated Pop, Evaluable Pop	16.2.6.9
14.2.9.4	Summary of PedsQL Physical Functioning Scale Score (Child Reports) and Change from Baseline by Questionnaire Age Group	All Treated Pop, Evaluable Pop	16.2.6.9
14.2.9.5	Summary of PedsQL Emotional Functioning Scale Score (Child Reports) and Change from Baseline by Questionnaire Age Group	All Treated Pop, Evaluable Pop	16.2.6.9
14.2.9.6	Summary of PedsQL Social Functioning Scale Score (Child Reports) and Change from Baseline by Questionnaire Age Group	All Treated Pop, Evaluable Pop	16.2.6.9
14.2.9.7	Summary of PedsQL Work/Study Functioning Scale Score (Child Reports 5-25 years) and Change from Baseline by Questionnaire Age Group	All Treated Pop, Evaluable Pop	16.2.6.9
14.2.10.1	Summary of BASES Questionnaire (Parent Reports)	All Treated Pop, Evaluable Pop	16.2.6.10
14.2.10.2	Summary of BASES Questionnaire (Nurse Reports)	All Treated Pop, Evaluable Pop	16.2.6.11
14.3 Safety	Data		
14.3.1.1.1	Summary of all Adverse Events	All Treated Pop	16.2.7.1.1
14.3.1.1.2	Summary of Adverse Events occurring prior to HSCT conditioning	All Treated Pop	16.2.7.1.2
14.3.1.1.3	Summary of Adverse Events occurring post HSCT conditioning	All Treated Pop	16.2.7.1.3
14.3.1.2.1	Summary of Adverse Events by System Organ Class and Preferred Term	All Treated Pop	16.2.7.1.1
14.3.1.2.2	Summary of non-SAEs by System Organ Class and Preferred Term	All Treated Pop	16.2.7.1.1
14.3.1.3	Summary of Adverse Events by Maximum Severity, System Organ Class and Preferred Term	All Treated Pop	16.2.7.1.1
14.3.1.4.1	Summary of Treatment-Emergent Adverse Events by System Organ Class and Preferred Term	All Treated Pop	16.2.7.1.1
14.3.1.4.2	Summary of Treatment-Emergent Adverse Events by Maximum Severity, System Organ Class and Preferred Term	All Treated Pop	16.2.7.1.1
14.3.1.4.3	Summary of Treatment-Emergent Adverse Events by Relationship to Study Drug, System Organ Class and Preferred Term	All Treated Pop	16.2.7.1.1

[figure not shown]

Table Number	Table Title / Summary	Population(s)	Supporting listing
14.3.1.5.1	Summary of Treatment-Emergent Adverse Events occurring prior to HSCT conditioning by System Organ Class and Preferred Term	All Treated Pop	16.2.7.1.2
14.3.1.5.2	Summary of Treatment-Emergent Adverse Events occurring prior to HSCT conditioning by Maximum Severity, System Organ Class and Preferred Term	All Treated Pop	16.2.7.1.2
14.3.1.5.3	Summary of Treatment-Emergent Adverse Events occurring prior to HSCT conditioning by Relationship to Study Drug, System Organ Class and Preferred Term	All Treated Pop	16.2.7.1.2
14.3.1.6.1	Summary of Treatment-Emergent Adverse Events occurring post HSCT conditioning by System Organ Class and Preferred Term	All Treated Pop	16.2.7.1.3
14.3.1.6.2	Summary of Treatment-Emergent Adverse Events occurring post HSCT conditioning by Maximum Severity, System Organ Class and Preferred Term	All Treated Pop	16.2.7.1.3
14.3.1.6.3	Summary of Treatment-Emergent Adverse Events occurring post to HSCT conditioning by Relationship to Study Drug, System Organ Class and Preferred Term	All Treated Pop	16.2.7.1.3
14.3.2.1	Summary of Treatment-Emergent Adverse Events Leading to Study Drug Withdrawal by Preferred Term	All Treated Pop	16.2.7.3
14.3.2.2	Summary of Treatment-Emergent Adverse Events Resulting in Death by Preferred Term	All Treated Pop	16.2.7.4
14.3.2.3.1	Summary of Serious Treatment-Emergent Adverse Events by System Organ Class and Preferred Term	All Treated Pop	16.2.7.2
14.3.2.3.2	Summary of Serious Treatment-Emergent Adverse Events occurring prior to HSCT conditioning by System Organ Class and Preferred Term	All Treated Pop	16.2.7.1.2 16.2.7.2
14.3.2.3.3	Summary of Serious Treatment-Emergent Adverse Events occurring post HSCT conditioning by System Organ Class and Preferred Term	All Treated Pop	16.2.7.1.3 16.2.7.2
14.3.2.4	Summary of Treatment-Emergent Adverse Events with Infusion-related Reactions by System Organ Class and Preferred Term	All Treated Pop	16.2.7.1.1
14.3.2.5.1	Summary of Treatment-Emergent Adverse Events with Infections occurring prior to HSCT conditioning by Severity, System Organ Class and Preferred Term	All Treated Pop	16.2.7.1.2
14.3.2.5.2	Summary of Treatment-Emergent Adverse Events with Infections occurring post to HSCT conditioning by Severity, System Organ Class and Preferred Term	All Treated Pop (only patients with start date of conditioning for HSCT)	16.2.7.1.3
14.3.5.1.1	Shift Table of Clinical Chemistry Results	All Treated Pop	16.2.8.1
14.3.5.1.2	Shift Table of Clinical Chemistry Results by Treatment Type	All Treated Pop	16.2.8.1

[figure not shown]

Table Number	Table Title / Summary	Population(s)	Supporting listing
14.3.5.2.1	Shift Table of Hematology Results	All Treated Pop	16.2.8.2
14.3.5.2.2	Shift Table of Hematology Results by Treatment Type	All Treated Pop	16.2.8.2
14.3.5.3.1	Shift Table of Coagulation Results	All Treated Pop	16.2.8.3
14.3.5.3.2	Shift Table of Coagulation Results by Treatment Type	All Treated Pop	16.2.8.3
14.3.6.1	Concomitant Medications for HLH Treatment by ATC Level 1 and Standardized Medication Term	All Treated Pop, Evaluable Pop	16.2.4.8
14.3.6.2	Concomitant Medications other than HLH Treatment by ATC Level 1 and Level 2	All Treated Pop, Evaluable Pop	16.2.4.9
14.3.6.3.1	Summary of Exposure to Emapalumab	All Treated Pop, Evaluable Pop	16.2.5.1 16.2.5.2
14.3.6.3.2	Percentage of Emapalumab Dose Changes from the Baseline Dose	All Treated Pop, Evaluable Pop	16.2.5.1 16.2.5.2
14.3.6.4	Summary of Serum Concentration of Emapalumab Levels	All Treated Pop	16.2.9.8.2
14.3.6.5	Summary of Pharmacodynamic Parameters	All Treated Pop	16.2.9.8.3
14.3.6.6	Summary of ADA Parameters	All Treated Pop	16.2.9.8.4

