4.1. Introduction

Data processing, tabulation of descriptive statistics, calculation of inferential statistics, and graphical representations will be performed primarily using SAS (release 9.4 or higher). If the use of other software is warranted, the final statistical methodology report will detail what software was used for what purposes.

Continuous (quantitative) variable summaries will include the number of patients (n) with non-missing values, mean, standard deviation, median, minimum, and maximum. The minimum and maximum will be reported with the same degree of precision (i.e., the same number of decimal places) as the observed data. Mean, standard deviation and median will be reported to 1 degree of precision more than the observed data.

Categorical (qualitative) variable summaries will include the frequency and percentage of patients who are in the particular category or each possible value. In general, the denominator for the percentage calculation will be based upon the total number of patients in the study population unless otherwise specified. Percentages will be rounded to 1 decimal place, unless otherwise

specified. Therefore, there may be cases where for instance the total of the percentages does not exactly equal 100%. In case confidence intervals are provided, they will be shown with 1 decimal place.

The number of missing values will be calculated as difference of the total number of subjects in the study population minus the number of non-missing values.

All p-values will be displayed to four decimals and rounded using standard scientific notation (e.g., 0.XXXX). If a p-value less than 0.0001 occurs it will be shown in tables as <0.0001.

All collected data will be presented in listings. Data not subject to analysis according to this plan will not appear in any tables or graphs but will be included only in the data listings.

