4.2. Interim Analysis and Data Monitoring

[figure not shown]
No interim analyses are planned.

An Independent Data Monitoring Committee (iDMC) has overall responsibility for safeguarding the interests of subjects by monitoring relevant data obtained in the study and making appropriate recommendations based on the reported data, thus ensuring that the study is being conducted with the highest scientific and ethical standards.

5. Analysis Sets

The following analysis populations are planned for this study:

- **Enrolled Analysis Set:** The Enrolled Population Analysis Set includes all patients who sign the informed consent form including screen failures. This population will be used only for the purpose of describing patient disposition and for protocol deviations (note: screen failures will be excluded in protocol deviation outputs).
- All Treated Analysis Set: The All Treated Analysis Set includes all patients who receive any part of an infusion of study drug. The All Treated Analysis Set will be the primary population for efficacy endpoints, and will be used for safety and PK/PD endpoints.
- Evaluable Analysis Set: The Evaluable Analysis Set includes all patients in the All Treated Analysis Set who have
 - Received a minimum of 3 consecutive infusions of emapalumab, not more than 6 days between infusions,
 - Not had a diagnosis of secondary HLH subsequent to the initiation of emapalumab treatment.
- Evaluable Analysis Set Without Major Protocol Deviations: The Evaluable Analysis Set Without Major Protocol Deviations includes all patients in the Evaluable analysis set who do not have a major protocol deviation that is deemed to have an impact on the statistical analysis.

Inclusion in the analysis sets defined above will be determined at a data review meeting before database lock.

6. General Issues for Statistical Analysis

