6.1.9.3. Safety Parameters

Table 4: Definition of Drug Administration Variables

Statistics for Exposure (dosing)	Derivation
Duration of exposure (days)	Date of last infusion of emapalumab – date of first infusion of emapalumab + 1
Duration of exposure (weeks)	Duration of exposure (days)/7
Maximum dose prescribed	Maximum of all doses prescribed (mg/kg)
Cumulative dose (mg/kg)	Sum of total actual dose per kg administered from first infusion date until last infusion date
Average dose frequency (days)	Duration of exposure (days)/ total number of infusions
Average dose of emapalumab per day (mg/kg)	Cumulative dose (mg/kg)/ duration of exposure (days)
Percentage of dose increases from baseline dose	(Number of dose increases from baseline dose / number of total doses) multiplied by 100.
Percentage of dose decreases from baseline dose	(Number of dose decreases from baseline dose / number of total doses) multiplied by 100.

Table 5: Definition of Adverse Events

Variable	Definition
Adverse Event (AE)	All recorded AEs (collection of AEs starts after ICF signature).
Treatment-Emergent Adverse Event (TEAE)	Any AE (serious and non-serious) with an onset date after the start of the first emapalumab infusion.
Pre-conditioning AE	Any AE (serious and non-serious) with start date before the start of conditioning for HSCT*.

[figure not shown]

Variable	Definition			
Post-conditioning AE	Any AE (serious and non-serious) with start date after the start of conditioning for HSCT*.			
TEAEs related to the study drug	Any AEs with an onset date after the start of the first emapalumab infusion with "Relationship to Study Drug" of "Related".			
Serious TEAEs	Any AEs with an onset date after the start of the first emapalumab infusion with "Serious" of "Yes".			
TEAEs leading to withdrawal of study drug	Any AEs with an onset date after the start of the first emapalumab infusion with "Action taken with study drug" of "Drug Withdrawn".			
TEAEs resulting in death	Any AEs with an onset date after the start of the first emapalumab infusion with "Results in death" of "Yes".			
TEAE with infections	Any AE with an onset date after the start of the first emapalumab infusion with system organ class (SOC) 'Infections and Infestations' or in the HLGT 'Microbiology and serology investigations'.			

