8.2.10. Quality of Life Assessed Through BASES Questionnaires

The BASES questionnaire scores for the 6 domains (note: activity and sleep subscales will be split into two separate domains due to differing best responses and exploratory nature of questionnaire) at the EOT and follow-up visits D+30, D+100, 6 months and 1 year will be

described using descriptive summaries of absolute values. BASES nurse and parent reports will be presented separately. Only patients with HSCT planned and/or performed will be analysed. Note: HSCT planned is defined as patients captured on the HSCT module of the eCRF with a start of conditioning date or on the CM module with HSCT conditioning medications as indicated in Appendix 15.3.

9. Supplementary Analysis

A supplementary analysis for Overall Response at EOT or Week 8 (whichever occurs earlier) using the definition of Overall Response in Table 7 will be performed. This will be evaluated using an exact binomial test as outlined in Section 8.1 and with the components of the overall response (Complete Response, Partial Response, HLH Improvement and No response) summarized using counts and percentages at Week 8 or EOT (whichever occurs first).

10. Safety and Tolerability Analysis

All safety analyses will be performed as specified in Table 3. All data relating to safety will be listed and summarized using descriptive statistics. No inferential statistical tests will be performed.

The analysis of safety assessments in this study will include summaries of the following categories of safety and tolerability data collected for each patient:

- Adverse events, treatment-emergent AEs (TEAEs), non-TEAEs, serious AEs (SAEs) and non-serious TEAEs
- Clinical laboratory parameters
- Vital signs

Where applicable, analyses will be performed separately for the pre and post-conditioning time periods and by treatment naïve/experienced (unless otherwise specified).

[figure not shown]
Data of patients who have not undergone HSCT will be analyzed in the pre-conditioning period.

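### Five post-conditioning adverse event tables default to all treated patients as denominator, while the post-conditioning infection table counts only patients who started conditioning

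*SAP*

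**What the plan says.** - **Populations.** In SAP Table 15 (section 14.1), five post-conditioning tables have the population All Treated Pop with nothing added. They are 14.3.1.1.3 ("Summary of Adverse Events occurring post HSCT conditioning"), 14.3.1.6.1 ("Summary of Treatment-Emergent Adverse Events occurring post HSCT conditioning by System Organ Class and Preferred Term"), 14.3.1.6.2 (by maximum severity), 14.3.1.6.3 (by relationship) and 14.3.2.3.3 (serious events). The post-conditioning infection table, 14.3.2.5.2, instead has "All Treated Pop (only patients with start date of conditioning for HSCT".
- **Default denominator.** SAP 4.1: "In general, the denominator for the percentage calculation will be based upon the total number of patients in the study population unless otherwise specified".
- **Who is in the set.** SAP section 5: "The All Treated Analysis Set includes all patients who receive any part of an infusion of study drug". Conditioning is not required.
- **What counts as an event.** SAP Table 5 defines a post-conditioning AE as "Any AE (serious and non-serious) with start date after the start of conditioning for HSCT".
- **Patients without transplant.** SAP section 10: "Data of patients who have not undergone HSCT will be analyzed in the pre-conditioning period".

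**The concern.** A patient who never starts conditioning cannot enter the numerator of a post-conditioning table but, under the default rule, stays in its denominator. The SAP expects such patients: proceeding to HSCT is itself a secondary endpoint, and the protocol provides follow-up for patients who are not transplanted.

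Two things are at stake. First, the SAP separates safety into pre- and post-conditioning periods so that each can be read on its own. A post-conditioning percentage diluted by patients who never entered the period does not describe that period. No wash-out is required between the last emapalumab infusion and conditioning, so events in this period are of interest. Second, the tables would disagree with each other. A post-conditioning infection TEAE belongs both in the general tables (14.3.1.6.1 and, by severity, 14.3.1.6.2) and in 14.3.2.5.2, over different denominators.

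Safety is also shown for treatment-naïve and treatment-experienced patients. If the share conditioned differs between these subgroups, equal rates among conditioned patients would print as unequal, or a real difference could be hidden.

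**Working it through.** The plan states no figure on this point, so there is none to reproduce. The check is a reading of the rules followed by one identity.

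**Reading**
1. Table 15 names the All Treated population for the five tables and specifies nothing further.
2. SAP 4.1 makes the total of the named population the denominator unless otherwise specified. SAP 10.1 and 10.1.2, which describe these summaries, set no other denominator.
3. Table 5 confines the numerator to events starting after the start of conditioning.
4. Section 10 says where the data of patients without HSCT are analysed. It does not say over whom the post-conditioning percentages are taken.
5. Only 14.3.2.5.2 carries the restriction.

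**Identity**
Let N be the number treated, m the number conditioned and x the number of patients with the event after conditioning. Then

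x/N = (x/m) × (m/N),

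so printed rate = rate among conditioned × share conditioned, and the relative understatement is 1 − m/N.

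**Inputs**
N = 34 is the planned minimum treated and 41 the maximum enrolled (SAP 3.2). The documents give no expected m. The shares below (about 50%, 70% and 90%) and the event counts are assumptions for illustration.

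| N | m | x | x/N | x/m | m/N |
|---|---|---|---|---|---|
| 34 | 17 | 5 | 14.7% | 29.4% | 0.50 |
| 34 | 24 | 12 | 35.3% | 50.0% | 0.71 |
| 34 | 31 | 16 | 47.1% | 51.6% | 0.91 |
| 41 | 20 | 10 | 24.4% | 50.0% | 0.49 |
| 41 | 29 | 14 | 34.1% | 48.3% | 0.71 |
| 41 | 37 | 18 | 43.9% | 48.6% | 0.90 |

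The understatement is therefore about 1 − 0.5 = 50% at the low end and 1 − 0.9 = 10% at the high end. If m = N it is zero.

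**Effect between tables**
In the second row, if the event is an infection, the same 12 patients appear as 12/34 = 35.3% in 14.3.1.6.1 and 12/24 = 50.0% in 14.3.2.5.2.

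**Effect between subgroups**
With the same 50% rate among conditioned patients, a subgroup with 50% conditioned prints 0.50 × 0.50 = 25%, and one with 90% conditioned prints 0.50 × 0.90 = 45%. These shares are also assumed.

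**The case against.** The strongest reply is that the population column in Table 15 names a parent analysis set and not a denominator. Survival post HSCT, duration of response and the BASES summaries are labelled All Treated and Evaluable without restriction, yet the SAP text narrows each of them. Sections 6.1.9.4 and 8.2.10 exclude, respectively, patients without HSCT, patients who never respond, and patients with no HSCT planned or performed. Section 10 could be read the same way, as keeping patients without HSCT out of the post-conditioning tables. The shells are a separate document, not available for this review, and may carry a denominator note.

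Part of this stands. The column alone does not settle the denominator, and a shell could. But each of those three examples has an explicit exclusion in the SAP text, and the five tables have none. If section 10 already removed these patients, the restriction written against 14.3.2.5.2 would be redundant.

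It is also fair that an all-treated percentage is a legitimate quantity, the risk per patient started on emapalumab. It answers a different question, and it does not explain why infections alone use the other denominator.

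A reader might infer that the plan understates transplant-period toxicity by a known and large amount, or that the tables cannot be compared at all. The documents support neither. The share conditioned is not given. Patient counts are reported, and SAP 10.8 provides a by-patient listing with the conditioning and HSCT dates, so the rate among conditioned patients can be recomputed. Table 14.2.7.3 is a less exact source because it counts patients with an HSCT date, who may be fewer than those conditioned.

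**Conclusion.** The inconsistency is real. Followed as written, the SAP computes percentages in five post-conditioning AE and SAE tables over all treated patients, and in the infection table over conditioned patients only. The relative understatement in the five equals the share not conditioned: about 50% to 10% for an assumed 50% to 90% conditioned, and none if all are conditioned. This rests on the SAP 4.1 default applying because nothing in the SAP text overrides it, and a note in the unseen shells could change that. Counts are correct either way. Safety is descriptive with no inferential tests, so no test or decision rule is affected. The change is worth making before the tables are produced, because it alters printed safety percentages at little cost. It is not evidence that the trial's safety conclusions would be wrong.

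**What to change.** 1. In Table 15, give 14.3.1.1.3, 14.3.1.6.1, 14.3.1.6.2, 14.3.1.6.3 and 14.3.2.3.3 the population already used for 14.3.2.5.2: "All Treated Pop (only patients with start date of conditioning for HSCT".
2. In the shells, print the number of patients conditioned as the column N, overall and for the treatment-naïve and treatment-experienced subgroups.
3. Reword the section 10 sentence so that assignment to a period depends on the conditioning start date and not on having undergone HSCT. At present, a patient conditioned but not transplanted has post-conditioning events under Table 5, while section 10 sends that patient's data to the pre-conditioning period. Copying the restriction into Table 15 without this step would leave that conflict in place.

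The cost is a minor SAP and shell edit with no new data. The post-conditioning percentages will look less favourable wherever some patients were not conditioned.
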